9.5. Programming Conventions

- Page orientation, margins, and fonts: Summary tables, listings, and figures will appear in landscape orientation. There should be a 1.0" boundary on the left and right edges. The top and bottom margins are 1.0" for tables and listings, but may vary for figures. Output should be printed in Courier New with a point size of 8.
- Identification of analysis population: Every summary table, listing, and figure will clearly specify the analysis population being summarized/listed. Listings will be prepared for all subjects randomized.
- Group headers: In the summary tables, the group headers will identify the within-group sample size for the indicated analysis population. Of note, the header's sample size does not necessarily equal the number of subjects actually summarized within any given summary module; some subjects in the analysis population may have missing values and thus may not be summarized.
- Suppression of percentages corresponding to null categories: When count data are presented as category frequencies and corresponding percentages, the percent should be suppressed when the count is zero in order to draw attention to the non-zero counts.
- Presentation of sample sizes: Summary modules should indicate, in one way or another, the number of subjects actually contributing to the summary statistics presented in any given summary module. As mentioned above, this may be less than the number of subjects in the analysis population.
 - ◆ In the quantitative modules describing continuous variables (and thus presenting sample size, means, and standard deviations), the sample size should be the number of non-missing observations
 - ◆ For categorical variables that are presented in frequency tables, the module should present the total count in addition to the count in each category. Percentages should be calculated using this total as the denominator, and the percentage corresponding to the sum itself (that is, 100%) should be presented so as to indicate clearly to a reviewer the method of calculation.
- Sorting: Listings will be sorted by treatment, subject number and date, if applicable. If a listing is sorted in a different manner, it will be indicated on the listing shells.
- General formatting rules: Rounding for all variables will occur only as the last step, immediately prior to presentation in listings, tables, and figures. No intermediate rounding will be performed on derived variables. The standard rounding practice of rounding numbers ending in 0-4 down and numbers ending in 5-9 up will be employed.
- The presentation of numerical values will adhere to the following guidelines:
 - ◆ Raw measurements will be reported to the number of significant digits as captured electronically or on the eCRFs.
 - ◆ Standard deviations will be reported to two decimal places beyond the number of decimal places the original parameter is presented.

- ◆ Means will be reported to the one decimal place beyond the number of decimal places the original parameter is presented.
- ◆ Calculated percentages will be reported with one decimal place.
- ◆ Coefficient of variation will be reported to the same number of decimal places as the standard deviation.
- Dates will be formatted as DDMMYY. Partial dates will be presented on data listings as recorded on eCRFs.
- Time will be presented according to the 24-hour clock (HH:MM).
- Verification of Results: All analyses will be subject to formal verification procedures. Specifically, results will be verified utilizing independent programming prior to issuance of the draft statistical report. All documents will be verified by the lead statistician to ensure accuracy and consistency of analyses.

9.7. Core Codes for imputation of MAR and MNAR

9.7.1. Imputation of Missing at Random (MAR) Cases

SAS PROC MI will be used to generate 27 possible imputed datasets using the following SAS code:

```
proc mi data=mcmc1 seed=SEED1 nimpute=27 out=Out1X;
mcmc chain=multiple displayinit initial=em(itprint);
var TRT y0 y1 y2 ... yn;
run;
```

Here, TRT is an indicator variable representing treatment with values of 'CVL-751' or 'Placebo', Y₁ - Y_N represent the response variable (e.g., 'ON' time without troublesome dyskinesias) for each visit, Y₀ is the baseline score, and SEED1 is a random number.

Each of these datasets will be analyzed using PROC MIXED in SAS using the MMRM model. The results of the analyses of the datasets will be combined using PROC MIANALYZE to produce an inferential result.

9.7.2. Imputation of Missing Not at Random (MNAR) Cases

The MNAR cases are imputed using reference based imputation (J2R) method. The five macros; SAS code for reference based multiple imputation [<https://www.lshtm.ac.uk/research/centres-projects-groups/missing-data#dia-working-group>] will be used to generate 27 possible imputed datasets using the following sample SAS code:

```
%include "&Path\part1A_33.sas";
%include "&Path\part1B_47.sas";
%include "&Path\part2A_40.sas";
%include "&Path\part2B_31.sas";
%include "&Path\part3_55.sas";
%include "&Path\plotter_7.sas";

%part1a(Jobname=X, Data=XX, Subject=usubjid, Response=aval, Time=avisitn, Treat=Trt01pn, cov=BASE, covgroup=trt01pn, Debug=1);
%part1b(Jobname=X, Ndraws=27, thin=350, seed=s, Debug=1);

%part2a(Jobname=X_J2R, inname=XX, method=J2R, ref=0, Debug=1);
%part2b(Jobname=X_J2R, seed=s, Debug=1);
```

Each of these datasets will be analyzed using PROC MIXED in SAS using the MMRM model. The results of the analyses of the datasets will be combined using PROC MIANALYZE to produce an inferential result.

9.8. CTCAE Based Laboratory Test Results Grading Specifications

Lab Test = Albumin

CTCAE Term	Grade 1	Grade 2	Grade 3	Grade 4	Grade 5
Hypoalbuminemia	<LLN - 3 g/dL; <LLN - 30 g/L	<3 - 2 g/dL; <30 - 20 g/L	<2 g/dL; <20 g/L	Life-threatening consequences; urgent intervention indicated	Death

Albumin will have grades 1-3,

- Grade 1 being any values from the LLN to 3 g/dL,
- Grade 2 from 2 to < 3 g/dL and
- Grade 3 < 2 g/dL

Lab Test = Amylase

CTCAE Term	Grade 1	Grade 2	Grade 3	Grade 4	Grade 5
Serum amylase increased	>ULN - 1.5 x ULN	>1.5 - 2.0 x ULN; >2.0 - 5.0 x ULN and asymptomatic	>2.0 - 5.0 x ULN with signs or symptoms; >5.0 x ULN and asymptomatic	>5.0 x ULN and with signs or symptoms	-

Amylase will have Grades 1, 2 and 3:

- Grade 1 being any values from the ULN to 1.5 x ULN
- Grade 2 from >1.5 to 5.0 x ULN
- Grade 3 from >5 x ULN

**Lab Test = Alkaline Phosphatase**

CTCAE Term	Grade 1	Grade 2	Grade 3	Grade 4	Grade 5
Alkaline phosphatase increased	>ULN - 2.5 x ULN if baseline was normal; 2.0 - 2.5 x baseline if baseline was abnormal	>2.5 - 5.0 x ULN if baseline was normal; >2.5 - 5.0 x baseline if baseline was abnormal	>5.0 - 20.0 x ULN if baseline was normal; >5.0 - 20.0 x baseline if baseline was abnormal	>20.0 x ULN if baseline was normal; >20.0 x baseline if baseline was abnormal	-

Alkaline Phosphatase will have grades 1-4 and grading is based ULN only.

- Grade 1 being any values from the ULN to 2.5 x ULN
- Grade 2 from >2.5 to 5.0 x ULN
- Grade 3 from >5.0 to 20.0 x ULN
- Grade 4 from >20.0 x ULN

Lab Test = Alanine Aminotransferase

CTCAE Term	Grade 1	Grade 2	Grade 3	Grade 4	Grade 5
Alanine aminotransferase increased	>ULN - 3.0 x ULN if baseline was normal; 1.5 - 3.0 x baseline if baseline was abnormal	>3.0 - 5.0 x ULN if baseline was normal; >3.0 - 5.0 x baseline if baseline was abnormal	>5.0 - 20.0 x ULN if baseline was normal; >5.0 - 20.0 x baseline if baseline was abnormal	>20.0 x ULN if baseline was normal; >20.0 x baseline if baseline was abnormal	-

ALT will have grades 1-4 and grading is based ULN only.

- Grade 1 being any values from the ULN to 3.0 x ULN
- Grade 2 from >3.0 to 5.0 x ULN
- Grade 3 from >5.0 to 20.0 x ULN
- Grade 4 from >20.0 x ULN

Lab Test = Aspartate Aminotransferase

CTCAE Term	Grade 1	Grade 2	Grade 3	Grade 4	Grade 5
Aspartate aminotransferase increased	>ULN - 3.0 x ULN if baseline was normal; 1.5 - 3.0 x baseline if baseline was abnormal	>3.0 - 5.0 x ULN if baseline was normal; >3.0 - 5.0 x baseline if baseline was abnormal	>5.0 - 20.0 x ULN if baseline was normal; >5.0 - 20.0 x baseline if baseline was abnormal	>20.0 x ULN if baseline was normal; >20.0 x baseline if baseline was abnormal	-

ALT will have grades 1-4 and grading is based ULN only.

- Grade 1 being any values from the ULN to 3.0 x ULN
- Grade 2 from >3.0 to 5.0 x ULN
- Grade 3 from >5.0 to 20.0 x ULN
- Grade 4 from >20.0 x ULN

Lab Test = Bilirubin

CTCAE Term	Grade 1	Grade 2	Grade 3	Grade 4	Grade 5
Blood bilirubin increased	>ULN - 1.5 x ULN if baseline was normal; > 1.0 - 1.5 x baseline if baseline was abnormal	>1.5 - 3.0 x ULN if baseline was normal; >1.5 - 3.0 x baseline if baseline was abnormal	>3.0 - 10.0 x ULN if baseline was normal; >3.0 - 10.0 x baseline if baseline was abnormal	>10.0 x ULN if baseline was normal; >10.0 x baseline if baseline was abnormal	-

Bilirubin will have grades 1-4 and grading is based ULN only

- Grade 1 being any values from the ULN to 1.5 x ULN
- Grade 2 from >1.5 to 3.0 x ULN
- Grade 3 from >3.0 to 10.0 x ULN
- Grade 4 from >10.0 x ULN

Lab Test = Corrected Serum Calcium

CTCAE Term	Grade 1	Grade 2	Grade 3	Grade 4	Grade 5
Hypocalcemia	Corrected serum calcium of <LLN - 8.0 mg/dL; <LLN - 2.0 mmol/L; Ionized calcium <LLN - 1.0 mmol/L	Corrected serum calcium of <8.0 - 7.0 mg/dL; <2.0 - 1.75 mmol/L; Ionized calcium <1.0 - 0.9 mmol/L; symptomatic	Corrected serum calcium of <7.0 - 6.0 mg/dL; <1.75 - 1.5 mmol/L; Ionized calcium <0.9 - 0.8 mmol/L; hospitalization indicated	Corrected serum calcium of <6.0 mg/dL; <1.5 mmol/L; Ionized calcium <0.8 mmol/L; life-threatening consequences	Death
Hypercalcemia	Corrected serum calcium of >ULN - 11.5 mg/dL; >ULN - 2.9 mmol/L; Ionized calcium >ULN - 1.5 mmol/L	Corrected serum calcium of >11.5 - 12.5 mg/dL; >2.9 - 3.1 mmol/L; Ionized calcium >1.5 - 1.6 mmol/L; symptomatic	Corrected serum calcium of >12.5 - 13.5 mg/dL; >3.1 - 3.4 mmol/L; Ionized calcium >1.6 - 1.8 mmol/L; hospitalization indicated	Corrected serum calcium of >13.5 mg/dL; >3.4 mmol/L; Ionized calcium >1.8 mmol/L; life-threatening consequences	Death

Calcium will have to be corrected for albumin using Payne's formula:

$$\text{Corrected calcium} = \text{measured Ca (mg/dL)} + 0.8 \times (4.0 \text{ g/dL} - \text{patient albumin (g/dL)}).$$

(NOTE: It should be confirmed with the lab whether or not the correction has already been applied).

The grading is in both directions High and Low. Both directions are graded in 4 categories as

Hypercalcemia

- Grade 1 being any values from the ULN to 11.5 mg/dL,
- Grade 2 from >11.5 to 12.5 mg/dL,
- Grade 3 from >12.5 to 13.5 mg/dL,
- Grade 4 >13.5 mg/dL

Hypocalcemia

- Grade 1 being any values from the LLN to 8.0 mg/dL,
- Grade 2 from 7.0 to <8.0 mg/dL,
- Grade 3 from 6.0 to <7.0 mg/dL,
- Grade 4 <6.0 mg/dL

**Lab Test = Cholesterol**

CTCAE Term	Grade 1	Grade 2	Grade 3	Grade 4	Grade 5
Cholesterol high	>ULN - 300 mg/dL; >ULN - 7.75 mmol/L	>300 - 400 mg/dL; >7.75 - 10.34 mmol/L	>400 - 500 mg/dL; >10.34 - 12.92 mmol/L	>500 mg/dL; >12.92 mmol/L	-

Cholesterol will have grades 1-4,

- Grade 1 being any values from the ULN to 300 mg/dL,
- Grade 2 from >300 to 400 mg/dL,
- Grade 3 from >400 to 500 mg/dL,
- Grade 4 >500 mg/dL

Lab Test = Creatine Kinase

CTCAE Term	Grade 1	Grade 2	Grade 3	Grade 4	Grade 5
CPK increased	>ULN - 2.5 x ULN	>2.5 x ULN - 5 x ULN	>5 x ULN - 10 x ULN	>10 x ULN	-

Creatine Kinase will have grades 1-4,

- Grade 1 being any values from the ULN to 2.5 x ULN ,
- Grade 2 from >2.5 to 5 x ULN ,
- Grade 3 from >5 to 10 x ULN ,
- Grade 4 >10 ULN

Lab Test = Creatinine

CTCAE Term	Grade 1	Grade 2	Grade 3	Grade 4	Grade 5
Creatinine increased	>ULN - 1.5 x ULN	>1.5 - 3.0 x baseline; >1.5 - 3.0 x ULN	>3.0 x baseline; >3.0 - 6.0 x ULN	>6.0 x ULN	-

Creatinine will have grades 1-4

- Grade 1 being any values from the ULN to 1.5 x ULN ,
- Grade 2 from >1.5 to 3.0 x ULN or >1.5 - 3.0 x baseline ,
- Grade 3 from >3.0 to 6.0 x ULN or >3.0 x baseline ,
- Grade 4 >6.0 x ULN

Lab Test = Fibrinogen

CTCAE Term	Grade 1	Grade 2	Grade 3	Grade 4	Grade 5
Fibrinogen decreased	<1.0 - 0.75 x LLN; if abnormal, <25% decrease from baseline	<0.75 - 0.5 x LLN; if abnormal, 25 - <50% decrease from baseline	<0.5 - 0.25 x LLN; if abnormal, 50 - <75% decrease from baseline	<0.25 x LLN; if abnormal, 75% decrease from baseline; absolute value <50 mg/dL	-

Fibrinogen will have Grades 1- 4:

- Grade 1 <1.0 - 0.75 x LLN
- Grade 2 <0.75 - 0.5 x LLN
- Grade 3 <0.5 - 0.25 x LLN
- Grade 4 <0.25 x LLN

Lab Test = Gamma-Glutamyl Transpeptidase

CTCAE Term	Grade 1	Grade 2	Grade 3	Grade 4	Grade 5
GGT increased	>ULN - 2.5 x ULN if baseline was normal; 2.0 - 2.5 x baseline if baseline was abnormal	>2.5 - 5.0 x ULN if baseline was normal; >2.5 - 5.0 x baseline if baseline was abnormal	>5.0 - 20.0 x ULN if baseline was normal; >5.0 - 20.0 x baseline if baseline was abnormal	>20.0 x ULN if baseline was normal; >20.0 x baseline if baseline was abnormal	-

Gamma-Glutamyl Transpeptidase will have grades 1-4 and based on ULN only

- Grade 1 being any values from the ULN to 2.5 x ULN ,
- Grade 2 from >2.5 to 5.0 x ULN
- Grade 3 from >5.0 to 20.0 x ULN
- Grade 4 from >20.0 x ULN

Lab Test = Glucose

CTCAE Term	Grade 1	Grade 2	Grade 3	Grade 4	Grade 5
Hyperglycemia	Abnormal glucose above baseline with no medical intervention	Change in daily management from baseline for a diabetic; oral antiglycemic agent initiated; workup for diabetes	Insulin therapy initiated; hospitalization indicated	Life-threatening consequences; urgent intervention indicated	Death
Hypoglycemia	<LLN - 55 mg/dL; <LLN - 3.0 mmol/L	<55 - 40 mg/dL; <3.0 - 2.2 mmol/L	<40 - 30 mg/dL; <2.2 - 1.7 mmol/L	<30 mg/dL; <1.7 mmol/L; life-threatening consequences; seizures	Death

Hypoglycemia will have grades 1-4,

- Grade 1 being any values from the LLN to 55 mg/dL,
- Grade 2 from 40 to <55 mg/dL,
- Grade 3 from 30 to <40 mg/dL,
- Grade 4 <30 mg/dL

Hyperglycemia will have one grade using the WHO criterion below

- Grade 1 >200 mg/dL;

Lab Test = Lipase

CTCAE Term	Grade 1	Grade 2	Grade 3	Grade 4	Grade 5
Serum lipase increased	>ULN - 1.5 x ULN	>1.5 - 2.0 x ULN; >2.0 - 5.0 x ULN and asymptomatic	>2.0 - 5.0 x ULN with signs or symptoms; >5.0 x ULN and asymptomatic	>5.0 x ULN and with signs or symptoms	-

Lipase will have Grades 1, 2 and 3:

- Grade 1 being any values from the ULN to 1.5 x ULN
- Grade 2 from >1.5 to 5.0 x ULN
- Grade 3 from >5 x ULN

Lab Test = Magnesium

CTCAE Term	Grade 1	Grade 2	Grade 3	Grade 4	Grade 5
Hypermagnesemia	>ULN - 3.0 mg/dL; >ULN - 1.23 mmol/L	-	>3.0 - 8.0 mg/dL; >1.23 - 3.30 mmol/L	>8.0 mg/dL; >3.30 mmol/L; life-threatening consequences	Death
Hypomagnesemia	<LLN - 1.2 mg/dL; <LLN - 0.5 mmol/L	<1.2 - 0.9 mg/dL; <0.5 - 0.4 mmol/L	<0.9 - 0.7 mg/dL; <0.4 - 0.3 mmol/L	<0.7 mg/dL; <0.3 mmol/L; life-threatening consequences	Death

Hypermagnesemia will have grades 1, 3, and 4,

- Grade 1 being any values from the ULN to 3.0 mg/dL,
- Grade 3 from >3.0 to 8.0 mg/dL,
- Grade 4 from >8.0 mg/dL

Hypomagnesemia will have grades 1 - 4,

- Grade 1 being any values from the LLN to 1.2 mg/dL,
- Grade 2 from 0.9 to <1.2 mg/dL,
- Grade 3 from 0.7 to <0.9 mg/dL,
- Grade 4 <0.7 mg/dL

Lab Test = Potassium

CTCAE Term	Grade 1	Grade 2	Grade 3	Grade 4	Grade 5
Hyperkalemia	>ULN - 5.5 mmol/L	>5.5 - 6.0 mmol/L; intervention initiated	>6.0 - 7.0 mmol/L; hospitalization indicated	>7.0 mmol/L; life-threatening consequences	Death
Hypokalemia	<LLN - 3.0 mmol/L	Symptomatic with <LLN - 3.0 mmol/L; intervention indicated	<3.0 - 2.5 mmol/L; hospitalization indicated	<2.5 mmol/L; life-threatening consequences	Death

Hyperkalemia will have grades 1-4,

- Grade 1 being any values from the ULN to 5.5 mmol/L,
- Grade 2 from >5.5 to 6.0 mmol/L,
- Grade 3 from >6.0 to 7.0 mmol/L,
- Grade 4 from >7.0 mmol/L

Hypokalemia will have grades 1, 3, and 4,

- Grade 1 being any values from the LLN to 3.0 mmol/L,
- Grade 3 from >2.5 to 3.0 mmol/L,
- Grade 4 <2.5 mmol/L

Lab Test = Sodium

CTCAE Term	Grade 1	Grade 2	Grade 3	Grade 4	Grade 5
Hypernatremia	>ULN - 150 mmol/L	>150 - 155 mmol/L; intervention initiated	>155 - 160 mmol/L; hospitalization indicated	>160 mmol/L; life-threatening consequences	Death
Hyponatremia	<LLN - 130 mmol/L	125-129 mmol/L and asymptomatic	125-129 mmol/L symptomatic; 120-124 mmol/L regardless of symptoms	<120 mmol/L; life-threatening consequences	Death

Hypernatremia will have grades 1-4,

- Grade 1 being any values from the ULN to 150 mmol/L,
- Grade 2 from >150 to 155 mmol/L,
- Grade 3 from >155 to 160 mmol/L,
- Grade 4 from >160 mmol/L

Hyponatremia will have grades 1-4,

- Grade 1 being any values from the LLN to 130 mmol/L,
- Grade 2 from 125 to <130 mmol/L,
- Grade 3 from 120 to <125 mmol/L,
- Grade 4 <120 mmol/L

Lab Test = Triglycerides

CTCAE Term	Grade 1	Grade 2	Grade 3	Grade 4	Grade 5
Hypertriglyceridemia	150 mg/dL - 300 mg/dL; 1.71 mmol/L - 3.42 mmol/L	>300 mg/dL - 500 mg/dL; >3.42 mmol/L - 5.7 mmol/L	>500 mg/dL - 1000 mg/dL; >5.7 mmol/L - 11.4 mmol/L	>1000 mg/dL; >11.4 mmol/L; life-threatening consequences	Death

Triglycerides will have grades 1-4,

- Grade 1 being any values from the 150 to 300 mg/dL,
- Grade 2 from >300 to 500 mg/dL,
- Grade 3 from >500 to 1000 mg/dL,
- Grade 4 from >1000 mmol/L

Lab Test = Uric Acid

CTCAE Term	Grade 1	Grade 2	Grade 3	Grade 4	Grade 5
Hyperuricemia	>ULN without physiologic consequences	-	>ULN with physiologic consequences	Life-threatening consequences	Death

Uric Acid will not be CTCAE graded.

Lab Test = Bicarbonate or CO₂

CTCAE Term	Grade 1	Grade 2	Grade 3	Grade 4	Grade 5
Blood bicarbonate decreased	<LLN and no intervention initiated	-	-	-	-

Bicarbonate or CO₂ will not be CTCAE graded.

Lab Test = Phosphorus or Phosphate

CTCAE Term	Grade 1	Grade 2	Grade 3	Grade 4	Grade 5
Hypophosphatemia	Laboratory finding only and intervention not indicated	Oral replacement therapy indicated	Severe or medically significant but not immediately life-threatening; hospitalization or prolongation of existing hospitalization indicated	Life-threatening consequences	Death
Hyperphosphatemia	Laboratory finding only and intervention not indicated	Noninvasive intervention indicated	Severe or medically significant but not immediately life-threatening; hospitalization or prolongation of existing hospitalization indicated	Life-threatening consequences; urgent intervention indicated (e.g., dialysis)	Death

Phosphorus or Phosphate will not be CTCAE graded.

Lab Test = Serum pH [This is not urine pH]

CTCAE Term	Grade 1	Grade 2	Grade 3	Grade 4	Grade 5
Acidosis	pH <normal, but >=7.3	-	pH <7.3	Life-threatening consequences	-
Alkalosis	pH >normal, but <=7.5	-	pH >7.5	Life-threatening consequences	-

Serum pH will be graded in both directions with Grades 1 and 3 only.

Acidosis Grade 1 .<LLN, but >=7.3 Grade 3, pH < 7.3

Alkaosis Grade 1 .>ULN, but <=7.5 Grade 3, pH < 7.5

Lab Test = Activated Partial Thromboplastin Time

CTCAE Term	Grade 1	Grade 2	Grade 3	Grade 4	Grade 5
Activated partial thromboplastin time prolonged	>ULN - 1.5 x ULN	>1.5 - 2.5 x ULN	>2.5 x ULN; bleeding	-	-

APTT will be graded in Grade 1-3

- Grade 1 being any values from the >ULN to 1.5 x ULN,
- Grade 2 from >1.5 to 2.5 x ULN,
- Grade 3 from >2.5 x ULN,

Lab Test = International Normalized Ratio

CTCAE Term	Grade 1	Grade 2	Grade 3	Grade 4	Grade 5
INR increased	>1.2 - 1.5; >1 - 1.5 x baseline if on anticoagulation; monitoring only indicated	>1.5 - 2.5; >1.5 - 2.5 x baseline if on anticoagulation; dose adjustment indicated	>2.5; >2.5 x baseline if on anticoagulation; bleeding	-	-

INR will be graded in Grade 1-3 without baseline factor

- Grade 1 being any values from the >1.2 to 1.5,
- Grade 2 from >1.5 to 2.5,
- Grade 3 from >2.5,

Lab Test = Eosinophils

CTCAE Term	Grade 1	Grade 2	Grade 3	Grade 4	Grade 5
Eosinophilia	>ULN and >Baseline	-	Steroids initiated	-	-

Eosinophils will not be CTCAE graded

Lab Test = Hemoglobin

CTCAE Term	Grade 1	Grade 2	Grade 3	Grade 4	Grade 5
Anemia	Hemoglobin (Hgb) <LLN - 10.0 g/dL; <LLN - 6.2 mmol/L; <LLN - 100 g/L	Hgb <10.0 - 8.0 g/dL; <6.2 - 4.9 mmol/L; <100 - 80g/L	Hgb <8.0 g/dL; <4.9 mmol/L; <80 g/L; transfusion indicated	Life-threatening consequences; urgent intervention indicated	Death
Hemoglobin Increased	Increase in > 0-2	Increase in >2-4g/dL	Increase > 4 g/DL	-	Death

Decreased Hemoglobin will have grades 1-3, with

- Grade 1 being any values from the LLN to 10 g/DL,
- Grade 2 from 8 to < 10 g/DL and
- Grade 3 < 8 g/DL

Increased Hemoglobin will not be graded.

Lab Test = CD4 Lymphocytes

CTCAE Term	Grade 1	Grade 2	Grade 3	Grade 4	Grade 5
CD4 lymphocytes decreased	<LLN - 500/mm3; <LLN - 0.5 x 10e9 /L	<500 - 200/mm3; <0.5 - 0.2 x 10e9 /L	<200 - 50/mm3; <0.2 x 0.05 - 10e9 /L	<50/mm3; <0.05 x 10e9 /L	-

Decreased CD4 count will have grades 1-4, with

- Grade 1 being any values from the LLN to 500/mm3,
- Grade 2 from <500 to 200/mm3 and
- Grade 3 from <200 to 50/mm3 and
- Grade 4 <50/mm3

Lab Test = Lymphocytes

CTCAE Term	Grade 1	Grade 2	Grade 3	Grade 4	Grade 5
Lymphocyte count decreased	<LLN - 800/mm3; <LLN - 0.8 x 10e9/L	<800 - 500/mm3; <0.8 - 0.5 x 10e9 /L	<500 - 200/mm3; <0.5 - 0.2 x 10e9 /L	<200/mm3; <0.2 x 10e9 /L	Lymphocyte count decreased
Lymphocyte count increased	-	>4000/mm3 - 20,000/mm3	>20,000/mm3	-	Lymphocyte count increased

Decreased Lymphocytes will have grades 1-4, with

- Grade 1 being any values from the LLN to 800/mm3,
- Grade 2 from <800 to 500/mm3 and
- Grade 3 from <500 to 200/mm3 and
- Grade 4 <200/mm3

Increase Lymphocytes will have grades 2 and 3 only, with

- Grade 2 from >4000 to 20,000/mm3 and
- Grade 3 >20,000/mm3

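### SAP 9.8, potassium: the hypokalemia Grade 3 rule has its strict inequality on the wrong bound, so 3.0 mmol/L meets two grades and 2.5 mmol/L meets none

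*SAP*

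**What the plan says.** The potassium entry in SAP 9.8 has two parts. The first is the CTCAE row for low potassium:

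- Grade 1: "Hypokalemia <LLN - 3.0 mmol/L"
- Grade 3: "<3.0 - 2.5 mmol/L; hospitalization indicated"
- Grade 4: "<2.5 mmol/L; life-threatening consequences"

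The second is the rule to be programmed, which uses only three of the grades and skips Grade 2:

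- The mildest category is given as "Grade 1 being any values from the LLN to 3.0 mmol/L"
- The next category in use is given as "Grade 3 from >2.5 to 3.0 mmol/L"
- The most severe category covers anything below 2.5 mmol/L, as in the row.

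The omission of Grade 2, which in CTCAE depends on symptoms or intervention, is stated openly and is not at issue.

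Two other sections use the grades. SAP 5.15.5 says that grading follows CTCAE Version 5.0 as specified in 9.8, and it builds a shift table from the baseline grade to the worst treatment-emergent grade. SAP 3.2.4.1 defines a treatment-emergent laboratory toxicity as a rise of one grade or more from baseline. Potassium is a required chemistry test (Protocol 10.2, Table 11).

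**The concern.** The rule should assign to each value the grade that the row above it assigns. It does not do so at either end of Grade 3. The row excludes 3.0 and includes 2.5, while the rule does the reverse. Grades 1 and 4 keep the row's limits at 3.0 and 2.5, so the reversal creates an overlap at the top of Grade 3 and a gap at the bottom.

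At stake is the safety summary of low potassium at the Grade 3 limits. A mild value could be tabulated as severe, and a value that CTCAE calls Grade 3 would be missing from the graded tables. Under SAP 5.15.5 the low/normal/high shift table is kept for parameters with no CTCAE grade, so potassium has no second shift table in which a missed 2.5 would appear.

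**Working it through.** The plan states no figure to reproduce. The check applies the two printed definitions to the same values and compares the results.

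**Inputs.** All bounds come from the potassium entry in SAP 9.8. Two inputs are not in the documents and are assumed: a reporting precision of 0.1 mmol/L, and the lower limit of normal (LLN), which was varied over 3.3, 3.4, 3.5 and 3.6 mmol/L.

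**Definitions, with K for potassium in mmol/L.**

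| Grade | CTCAE row | Implementation rule |
|---|---|---|
| 1 | 3.0 ≤ K < LLN | 3.0 ≤ K < LLN |
| 3 | 2.5 ≤ K < 3.0 | 2.5 < K ≤ 3.0 |
| 4 | K < 2.5 | K < 2.5 |

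The Grade 1 bullet is read here as excluding the LLN itself, in line with the row.

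**Result around the limits (LLN assumed 3.5).**

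| K | Row | Rule |
|---|---|---|
| 3.1 | 1 | 1 |
| 3.0 | 1 | 1 and 3 |
| 2.9 | 3 | 3 |
| 2.6 | 3 | 3 |
| 2.5 | 3 | none |
| 2.4 | 4 | 4 |

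On the grid from 2.0 to 3.6 mmol/L, 3.0 and 2.5 are the only values on which the rule and the row disagree. This holds for each of the four assumed LLNs. Finer reporting precision would not add discordant values, because the two definitions differ only at those two points.

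**Is there a reading that removes the conflict?** Suppose that Grade 1 stops short of 3.0. The overlap then goes, but 3.0 becomes Grade 3 only, which still contradicts the row, and 2.5 still has no grade.

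**Is it a house convention?** For low-direction tests written in ascending order, 9.8 elsewhere includes the lower bound and excludes the upper one. Hypomagnesemia has "Grade 2 from 0.9 to <1.2 mg/dL"; calcium Grade 3 is 6.0 to <7.0 mg/dL, hypoglycemia Grade 3 is 30 to <40 mg/dL, and hyponatremia Grade 3 is 120 to <125 mmol/L. A strict lower bound with an inclusive upper bound is the form that 9.8 uses for high-direction tests, such as hyperkalemia Grade 3 at >6.0 to 7.0 mmol/L. The hypokalemia bullet therefore has the shape of a high-direction rule.

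**Effect on the derived variables.** With a normal baseline, a later 2.5 has no grade and so is not a treatment-emergent toxicity under SAP 3.2.4.1; under the row it would be Grade 3. With a normal baseline, a later 3.0 is treatment-emergent either way, but its grade could be 1 or 3 depending on the code.

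**After correction.** With Grade 3 as 2.5 to <3.0, a value of 3.0 is Grade 1 only, 2.5 is Grade 3, and every value below the LLN has exactly one grade.

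**The case against.** The mismatch between rule and row is not in real dispute. The serious objections concern its consequences.

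*A reader might infer that the worst-grade shift table necessarily reports 3.0 two grades too high.* The documents do not support that. SAP 5.15.5 takes the worst grade across a subject's treatment-emergent results. It does not say which grade applies when one result satisfies two. Code that tests Grade 1 first and stops would give Grade 1; code in which the later test overwrites the earlier one would give Grade 3. The supportable statement is that 3.0 could be counted as Grade 3.

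*A reader might infer that a 2.5 is reported as no toxicity at all.* That is too broad. SAP 5.15.5 still flags the value low against the central laboratory range and lists it. It still meets the separate definition of a treatment-emergent laboratory abnormality in SAP 3.2.4.1. Protocol 8.3.7 and 10.2 require clinically significant abnormalities to be recorded as adverse events. The loss is confined to the CTCAE-graded summaries.

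*The full row stands above the rule, and SAP 9.5 requires independent programming.* This lowers the chance of a wrong table, and a below-range result with no grade might well be noticed. But two programmers who follow the same bullets would both leave 2.5 ungraded, so verification cannot be relied on to correct the specification.

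*Read literally, the Grade 1 bullet also covers a value equal to the LLN, which the row does not grade.* This is fair, and it is why the count of two discordant values carries the reading stated in the working. It bears on neither Grade 3 limit.

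*Section 9.8 has other slips of this kind.* Triglycerides Grade 4 is given in mmol/L beside a row threshold of 1000 mg/dL, and alkalosis Grade 3 is written as pH below 7.5 where the row has above 7.5. This is a reason to proofread the whole section, not to leave potassium as it is.

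**Conclusion.** The rule is wrong as written: it is inconsistent with the CTCAE row that it implements. The finding rests only on bounds printed in the SAP. It is a transcription error in a grading specification and not a miscalculation, and nothing in 9.8 presents it as a deliberate departure from CTCAE.

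The size is small. Only results of exactly 3.0 or 2.5 mmol/L are affected, and the schedule in Protocol 1.3 has post-baseline safety bloods at Weeks 11, 22 and 27 only, apart from early-termination or unscheduled samples. The documents give no potassium distribution, so no expected count can be derived. The assumptions are reporting to 0.1 mmol/L, an LLN between 3.3 and 3.6 mmol/L, and Grade 1 read as starting below the LLN. No efficacy result, power or alpha figure depends on it. It is a desirable correction and not a critical one.

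**What to change.** In the potassium entry of SAP 9.8, rewrite the Grade 3 bullet for hypokalemia as 2.5 to <3.0 mmol/L. Keep 3.0 in Grade 1 and leave Grade 4 as <2.5. This restates the SAP's own CTCAE row in the form used by the other low-direction tests.

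The cost is moving one inequality sign in the SAP and making the same change in the grading program, if it has been written. No data collection or other analysis is touched. A single proofreading pass comparing each rule in 9.8 with its row could be done at the same time.
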